Observing the participant

Receiving an unsolicited complaint from the participant/family. Participants/families will have study contact information including a monitored phone number to report AEs. We will also provide advice on whether urgent medical attention is required, even though this would be expected to be a rare event.

Follow up phone call above.

Grading of Adverse Events Other than Systemic Allergic Reactions: The study sites will grade the severity of non-allergic adverse events experienced by the study participants according to the criteria set forth in the FDA Guidance for Industry Toxicity Grading Scale for Healthy Adult and Adolescent Volunteers Enrolled in Preventive Vaccine Clinical Trials (September 2007); hereafter, referred to as the FDA Toxicity Grading Scale. Adverse events will be graded on a scale from 1 to 5 according to the following standards in the FDA Toxicity Grading Scale:

- Grade 1 = Mild
- Grade 2 = Moderate
- Grade 3 = Severe
- Grade 4 = Life-threatening
- Grade 5 = Death

Grading of Systemic Allergic Reactions:

The investigator will grade severity of systemic allergic reactions on a scale of 1 to 5 according to criteria set forth in the CoFAR Grading Scale.

CoFAR Grading Scale for Systemic Allergic Reactions Version 3.0:

Grade 1: Reaction involving one of the following organ systems in which the symptoms are mild:

- Cutaneous: Generalized pruritus, generalized urticaria, flushing, angioedema
- Upper respiratory: Rhinitis, cough unrelated to laryngeal edema or bronchospasm
- Conjunctival: Injection/redness, itching, tearing
- GI: Nausea, abdominal pain (no change in activity level), single episode of vomiting and/or single episode of diarrhea

Grade 2: Reaction involving two or more of the following organ systems in which the symptoms are mild:

- Cutaneous: Generalized pruritus, generalized urticaria, flushing, angioedema
- Upper respiratory: Rhinitis, cough unrelated to laryngeal edema or bronchospasm
- Conjunctival: Injection/redness, itching, tearing
- GI: Nausea, abdominal pain (no change in activity level), single episode of vomiting, and/or single episode of diarrhea

OR

Reaction involving at least one of the following organ systems in which the symptoms are moderate:

- Cutaneous: Generalized pruritus, generalized urticaria, flushing, angioedema

- Upper respiratory: Rhinitis, cough unrelated to laryngeal edema or bronchospasm
- Conjunctival: Injection/redness, itching, tearing
- GI: Nausea, abdominal pain (with change in activity level), two episodes of vomiting and/or diarrhea

Grade 3: Reaction involving one or more of the following organ systems:

- Lower respiratory: Throat tightness, wheezing, chest tightness, dyspnea, cough that respond to short acting bronchodilator treatment (including IM epinephrine) with or without supplemental oxygen
- GI: Severe abdominal pain, more than two episodes of vomiting and/or diarrhea
- Cardiovascular: Reduced BP with lightheadedness, presyncope or tachycardia

Grade 4: Life-threatening reaction involving one or more of the following organ systems with or without other symptoms listed in Grades 1 to 3:

- Lower respiratory: Throat tightness with stridor, wheezing, chest tightness, dyspnea, or cough associated with a requirement for supplemental oxygen and refractoriness to short-acting bronchodilator treatment (including IM epinephrine)¹
OR
- Respiratory compromise requiring mechanical support
- Cardiovascular: Reduced BP with associated symptoms of end-organ dysfunction (e.g., hypotonia [collapse], syncope) defined as: systolic BP of less than 90 mmHg or >30% decrease from baseline

Grade 5: Death

1. Examples of refractoriness could include continuous albuterol nebulizer or epinephrine IV infusion or more than three IM epinephrine injections

The investigator will also grade likelihood of systemic allergic reactions according to criteria set forth by the Brighton Collaboration case definition and guidelines for anaphylaxis. Please see attached supporting documents in Section 44.

Recording/Monitoring:

Throughout the study, the investigator will record adverse events and serious adverse events on the appropriate AE/SAE electronic Case Report Form (eCRF) regardless of the relationship to the OFC or study procedure. Once recorded, an AE/SAE will be followed until it resolves with or without sequelae, or the AE/SAE stabilizes, or until 1 days after the participant's OFC, whichever occurs first.

Attribution of Adverse Events Code Descriptor Relationship

RELATED CATEGORIES

1. Definitely Related
2. Probably Related
3. Possibly Related

NOT RELATED CATEGORY

4. Unlikely to be Related
5. Definitely not Related

Reporting:

We will report any adverse events and other reportable incidences and occurrences (ORIO) to the IRB. Any adverse event or ORIO will be documented of that event including a description, subject number, date, outcome, and follow-up. Reporting of adverse events and ORIOs will follow IRBMED's reporting timetable and will occur at least yearly.

Statistical Design

Stopping rules. The anaphylaxis prediction threshold used in the study 2 trial will be data-driven based on results from our ongoing data collection study. We will perform a series of logistic regression models testing the predictive value of various levels of absolute increases in TEWL, thresholds of TEWL and their combinations. These will be tested against time to first symptom, time to formal anaphylaxis diagnosis, time to first medication use, and time to epinephrine use. To avoid overfitting, these analyses will use a 2:1 derivation: validation random split. Corrections will include baseline TEWL value and variance. A minimum sustained timespan meeting the threshold (such as 30-60 seconds) may be needed to minimize the effects of noise in the measurement.

Endpoints. The primary endpoint will be anaphylaxis rate among the intervention group versus the control group and will be reported with a 95% confidence interval. Secondary endpoints will include anaphylaxis severity and overall reaction rates. Exploratory endpoints may include but are not limited to time to first treatment, time to first symptom, epinephrine use, any medication use, and time to meeting a stopping rule (regardless of whether it was implemented); all will be reported with 95% confidence intervals. Exact p-values will be calculated using Fischer's test.

Descriptive analyses. Descriptive analyses will be reported. Continuous baseline measures will be reported using either mean (or geometric mean) with 95% confidence interval or median with first and third quartiles, as appropriate. Categorical baseline and demographic characteristics and study disposition will be reported as frequencies and proportions.

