Objectives: Primary Objective: *Define anaphylaxis rates in OFCs for peanut allergy halted by TEWL stopping rules plus standard of care clinical assessment versus control OFCs, where challenges are halted based only on clinical assessment of reaction status per standard of care.*

Secondary Objectives:

1. Define overall allergic reaction rates in peanut OFCs halted by TEWL stopping rules versus usual care.
2. Define anaphylaxis likelihood and severity via Brighton and CoFAR criteria among anaphylaxis reactions in peanut OFCs halted by TEWL stopping rules versus usual care.

Endpoints: Primary Endpoint: Anaphylaxis occurrence rate

Secondary Endpoints: Secondary endpoints will include anaphylaxis severity and overall allergic reaction rates.

Anaphylaxis likelihood will be defined by the Brighton criteria. Anaphylaxis severity will be defined via the modified CoFAR criteria (these are defined in the protocol).

Study Population: The total study population will be 40 individuals aged 6 months to 5 years, any gender, any demographic group, with a high likelihood of peanut allergy (defined in protocol). The study will take place in Michigan.

Phase: N/A

Description of Sites/Facilities This will be a single center study at the University of Michigan in Ann Arbor, MI.

[figure not shown]
Enrolling Participants:

Description of Study Intervention: This study will evaluate the use of transepidermal water loss (TEWL) continuous measurement during oral food challenge for food allergy (peanut). A stopping rule based on TEWL will be tested against usual oral food challenge care. In both cases, the standard of care will be used, where even a single symptom of an allergic reaction is used to stop oral food challenges. TEWL measures the rate of water loss from the skin in $\text{g}/\text{m}^2/\text{h}$ as a flux of water mass through an area over time.

Study Duration: 24 months

Participant Duration: Up to 9 days

Schema

Schedule of Activities

Procedures	Screening Day -7 to -1	OFC visit Visit 1, Day 1	Check-in Day 2	call,
Pre-screening questions	X			
Informed consent	X			
Confirm eligibility	X	X		
Demographics	X			
Medical history	X			
Randomization	X			
Administer study OFC		X		
Concomitant medication review	X			
Physical exam (including height and weight)		X		
Vital signs		X		
Weight		X		
Adverse event review and evaluation	X	X	X	
Complete Case Report Forms (CRFs)	X	X	X	

1. Objective

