This will be an open OFC, meaning participants will know they are eating a likely reactive food. To be clear, an alternative approach is to perform double-blinded, placebo-controlled (DBPC) OFCs; this means the participant does two OFCs in which they receive placebo and the food in question in two separate challenges (usually a day to a week apart) and are blinded to which is done on each day. Blinding food compounds are used to obscure the food, such as applesauce or mint chocolate. While the DBPC OFC is considered the most definitive OFC method, the open OFC is considered an appropriate criterion standard and is in fact the method used clinically across the US ^{69,70}. Thus, given the markedly increased costs of DBPC OFCs and the lack of their use in FA clinics, we will use the open OFC in this pilot study.

Blinding procedures.

Participants and families, the food allergy nurse administering the OFC, and the allergist physician assessing and treating the patient will be blinded to the study arm status (i.e., TEWL stopping rule intervention group

or control group). The study coordinator monitoring TEWL during the OFC will need to know the intervention arm vs control arm status to declare the OFC ceased when stopping rules are reached; this person will have no say in assessment or treatment of reactions. The study coordinator monitoring TEWL will be in the same room as the participant but will be behind a screen so that the screen displaying the TEWL results and the study coordinator's face will not be immediately visible to the other team members. All subjects will have TEWL monitored throughout to control for confounding factors associated with having a monitoring device on the skin. At the end of the OFC, after the determination of OFC outcomes, the participants and families will be made aware of the overall OFC determination of allergy status.

Regardless of group assignment (TEWL stopping rule or usual care with TEWL simply measured but not reported during the OFC), we expect that participants will be able to use the results of the OFC to reliably define true clinical food allergy status. Diagnosis will rely on standard of care in both cases.

Randomization.

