Participants will be randomized 1:1 to the intervention and control groups. We will use permuted block randomization. We will vary the block size from 2 to 4 in order to enhance blinding. We will upload a 40-person participant list to randomization software that will produce the randomization, which will be performed at visit 1 (initial screening visit) or no later than the day of the research food challenge. The TEWL study coordinator will learn the group designation for each participant at the start of that participant's challenge by the software.

TEWL measurement methods.

All subjects will undergo continuous TEWL measurement ^{48,54}. We will use a Tewameter VT310 device (Khazaka, Germany); these probes and supporting software were supplied at no cost and with no obligation except mention of material support in publications by the manufacturer. Measurements are taken using a small adhesive to attach the probe to the skin. Measurements are taken on the volar forearm. Data are collected in MPA CT Plus software (Khazaka, Germany) which provides note-taking functions and exports data into Microsoft Excel (Seattle, WA) for analysis.

Adjudication of OFC results.

A FA physician will adjudicate reactions and diagnose anaphylaxis identically to usual care in the FA clinic. The Brighton anaphylaxis likelihood scale will be used to assess anaphylaxis likelihood. The decision tree is copied here (next page, Figure 3). The CoFAR anaphylaxis severity scale will be used for anaphylaxis severity⁷¹ and is below in the adverse event grading section of the protocol. The Brighton score gives a 0-3 score of anaphylaxis likelihood (0 = no anaphylaxis, 3 = highly likely). The CoFAR severity score gives a grade of 1-5 of anaphylaxis severity (where 1 = mild, 5 = death).

Any symptom typical of food allergy (see Brighton and CoFAR scales) will count as a reaction, consistent with standard of care diagnosis for peanut allergy. Note that this is distinct from anaphylaxis.

TEWL-based stopping rules will be applied to the intervention group. We plan to use a 1 g/m²/h increase in TEWL value averaged over the 2 minute period after a fully-consumed food dose versus the 2 minute period averaged over the period just prior to that food dose. If the individual meets this threshold, at the first sign of a clinical symptom, the food challenge will be stopped.

[figure not shown]

Figure 3: Brighton Anaphylaxis Likelihood Scale

PrePARE Trial v2.2, 30 November 2022

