Treatment of reactions.

Reaction treatment will be based on symptoms assessed by the allergist per the clinical standard of care. If the participant meets anaphylaxis criteria ⁷¹, then weight-based anaphylaxis epinephrine dosing will be given, with a follow-up dose 5 minutes later if symptoms do not resolve. Albuterol via nebulizer or inhaler/mask (depending on age) and liquid diphenhydramine and cetirizine (both are antihistamines and use weight-based dosing) will be available and used after epinephrine in the case of anaphylaxis. All doses will be calculated prior to the challenge. If a participant has a reaction not meeting anaphylaxis criteria (i.e., they only have hives but no additional symptoms), the physician may choose to stop the OFC and give an antihistamine. If the TEWL-based stopping rule is invoked, the OFC will be stopped (no more food doses given); if the participant meets anaphylaxis criteria at that time, epinephrine will be given, otherwise an antihistamine dose will be given per standard of care.

Table 2: Outcome measures		Definition
Primary outcome	Anaphylaxis rate	Any Brighton Level 1, 2, or 3 anaphylaxis (see table above)
Secondary outcomes	Reaction rate	Any objective symptom of allergic reaction occurs (e.g., hives, angioedema, vomiting, wheeze, etc) not rising to the definition of anaphylaxis.
	Anaphylaxis severity	CoFAR score, defined below
	Anaphylaxis likelihood	Brighton score, defined above
Exploratory endpoints (Partial list)	Time to first symptom	Time from first food dose to any symptom
	Reaction symptoms	All reaction symptoms listed
	Epinephrine use	Any epinephrine administration
	Any medication use	Any medication administration
	Time to stopping rule	Time in minutes to stopping rule trigger

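### The assessing allergist is described as blinded although a recognised TEWL stop would reveal the intervention arm, and the primary endpoint has two definitions

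*Combined protocol and SAP*

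**What the plan says.** **Blinding.** Under Blinding procedures: "Participants and families, the food allergy nurse administering the OFC, and the allergist physician assessing and treating the patient will be blinded" to arm. The coordinator who watches TEWL knows the arm in order "to declare the OFC ceased when stopping rules are reached". Three safeguards are given there: a screen hides the coordinator's face and the TEWL display, TEWL is monitored in every child, and the coordinator has no say in assessing or treating reactions. The control condition is "usual care with TEWL simply measured but not reported during the OFC". Under Randomization: "We will vary the block size from 2 to 4 in order to enhance blinding".

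**Stopping.** Under Adjudication of OFC results: "TEWL-based stopping rules will be applied to the intervention group", and then "If the individual meets this threshold, at the first sign of a clinical symptom, the food challenge will be stopped". The synopsis says that in both arms "even a single symptom of an allergic reaction is used to stop oral food challenges". Under Treatment of reactions, for a reaction short of anaphylaxis, "the physician may choose to stop the OFC and give an antihistamine". That section gives an invoked TEWL rule its own path and does not repeat the symptom condition.

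**Endpoint.** Table 2 defines the primary outcome as Brighton Level 1, 2 or 3. The Outcome measures text says anaphylaxis follows current practice parameters, which it summarises as broadly two symptoms or a fall in blood pressure. A food allergy physician adjudicates as in usual care. The visible text describes no masked adjudication.

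**The concern.** The Background section itself says that anaphylaxis is a purely clinical diagnosis made by observation. If the physician who makes that call can tell that a stop came from the TEWL rule, the arm is known while the outcome is still open to judgement. Direct unmasking by this route can happen only in the intervention arm, so any effect on the call would not balance between arms.

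The direction could go either way. A physician who sees that the challenge was halted early might be less ready to call anaphylaxis, or more alert to it. The first would favour TEWL and the second would work against it.

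The two endpoint definitions are a separate problem, which stands even if no stop is ever recognised. A child could count as an event under one and not under the other, and the analysis could use either.

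**Working it through.** **1. Does a TEWL stop identify the arm?** The rule is applied to the intervention group only, and control TEWL is not reported during the challenge. No sham stop in controls is described. So if a stop is recognised as TEWL-declared, the child is in the intervention arm. The screen hides the coordinator's face and the display, but not the declaration. Treatment of reactions also sets one path for an invoked TEWL rule (stop, then an antihistamine unless anaphylaxis criteria are met) and a discretionary one for other non-anaphylactic reactions. A physician can follow these as separate paths only by knowing that the rule was invoked.

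**2. How recognisable is such a stop?** Three places bear on this:

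| Place | Content | Implication |
|---|---|---|
| Synopsis | A single symptom is used to stop in both arms | A TEWL stop could look like a clinical stop |
| Adjudication of OFC results | A TEWL stop needs the threshold and a symptom | Same |
| Treatment of reactions | A clinical stop is discretionary; the symptom condition is not repeated for a TEWL stop | A TEWL stop could stand out |

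The text does not settle the question, and it does not say how a stop is announced.

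**3. The plan's own figure.** Inputs from Population size: 80% v 30%, two-sided alpha 0.05, Fisher's exact test, 1:1, 19 per group. Enumerating both binomials and rejecting when p ≤ 0.05 gives power of 79.2% at 17 per group, 83.5% at 18 and 85.2% at 19. The continuity-corrected formula gives 19, and 38 / 0.95 = 40. The sample size is not at fault.

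**4. Under-calling when TEWL has no effect.** Let f be the share of intervention-arm events in unmasked children and m the share of those events called non-anaphylaxis. Both are assumptions. Control rate 0.80; apparent intervention rate 0.80 × (1 − f × m); 19 per arm. The result is the chance of a significant difference favouring TEWL. With m = 0 it is 1.1%.

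| f | m = 10% | m = 20% | m = 30% |
|---|---|---|---|
| 0.5 | rate 0.76: 2.3% | 0.72: 4.2% | 0.68: 7.3% |
| 1 | rate 0.72: 4.2% | 0.64: 11.8% | 0.56: 25.5% |

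**5. Over-calling when the planned effect is real.** Control 0.80, true intervention 0.30, so 70 points are non-events. Not all of these can be unmasked. The benefits section expects 20% of both groups to pass, and the Outcome measures text counts any implemented stop as a positive challenge, so a child who passes had no TEWL stop. At most 70 − 20 = 50 points can be unmasked.

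- Half of non-events unmasked (35 points): rate 0.30 + 0.35 × m.
- Ceiling (50 points): rate 0.30 + 0.50 × m.

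| Case | m = 10% | m = 20% | m = 30% |
|---|---|---|---|
| Half | rate 0.335: power 79% | 0.37: 72% | 0.405: 64% |
| Ceiling | rate 0.35: power 76% | 0.40: 65% | 0.45: 52% |

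With m = 0, power is 85%.

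**6. Endpoint.** Table 2 and the Outcome measures text name different criteria for the same outcome, and no passage ranks them. How many children would be classified differently cannot be worked out: the Brighton tree (Figure 3) is not visible and the practice parameters are only cited.

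**The case against.** The strongest reply is that a TEWL stop may never be noticed. It needs a symptom, a symptom already stops challenges in both arms according to the synopsis, every child wears the probe, and the coordinator is screened off and takes no part in assessment. The appendix on challenge conduct was not visible and might say how stops are announced. This stands as a limit on the claim: recognition is plausible, not certain, and cannot be counted. It does not remove the concern, because the safeguards leave the declaration itself open and Treatment of reactions writes a separate path for it.

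The synopsis could also be read as saying what may suffice to stop, which would fit physician discretion. In that case TEWL stops would be more distinguishable, not less.

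On the endpoint, Table 2 is the only place with a column headed as a definition, and the practice-parameter summary is worded loosely. That is a good reason to prefer Table 2, but the plan does not say so.

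Some stronger readings do not hold:

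- A reader might infer that the allergist is in practice unblinded, or that the result will be biased towards TEWL. The documents give neither the number of recognised stops nor a direction.
- A reader might count the usual-care adjudication sentence as a third definition. It says who adjudicates and how, and the Brighton scale follows directly.
- A reader might infer from the short blocks that control allocations can be deduced. The plan does not say that staff know the block sizes, and randomization may take place at screening or as late as the challenge day, so challenge order need not follow list order.

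**Conclusion.** Both parts hold, with different firmness. The endpoint conflict is plain in the text. The blinding problem is conditional: if a stop is recognised as TEWL-declared, the intervention arm is revealed to the person making a judgement-based primary call, and the visible plan has nothing that prevents this.

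The size is unknown. The worked scenarios rest on assumed unmasked shares and miscalling rates of 10 to 30%, at 19 per arm. They show a small effect if few children are unmasked or few calls change, and a material one if many are: up to a 25.5% chance of a significant result favouring TEWL when it has no effect, or power as low as 52% when the planned effect is real. These are bounds on the assumptions, not predictions. Correcting both points is advisable. Neither invalidates the pilot.

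**What to change.** 1. Make Table 2's Brighton Level 1, 2 or 3 the single primary definition and align the Outcome measures text with it.
2. Assign it by applying the protocol's Brighton decision tree as a fixed rule to the recorded signs and times, with arm, TEWL trace and stop reason removed. Report the bedside physician's diagnosis as a sensitivity analysis.
3. Record for each child whether the stop was TEWL-declared or clinical, and report counts by arm. The TEWL-declared count is an upper bound on direct unmasking.
4. Restate blinding of the assessing team as not assured after a TEWL stop.
5. Reconcile the synopsis, Adjudication of OFC results and Treatment of reactions on when a challenge stops and whether a TEWL stop needs a symptom. Which rule is right is for the investigators. Use a stop announcement that gives no reason only if the reconciled text allows it without altering the treatment path.

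The cost is a structured sign checklist, one case report form item, a short program and wording changes, with no extra assessor. Signs would still be recorded at the bedside by a team that may be unmasked, so bias is reduced and not removed. Use of the tree as a fixed rule rests on the protocol calling Figure 3 a decision tree, since the figure was not visible.

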**Predicting Peanut Anaphylaxis and Reducing
Epinephrine (PrePARE)**

NCT05696236

Date of IRB Approval: September 11, 2023

Title: Transepidermal Water Loss as a Predictor for Severe Allergic Reactions in Oral Food Challenges

Short Title: Predicting peanut anaphylaxis and reducing epinephrine

Acronym: PrePARE

Protocol Number: HUM00205852

National Clinical Trial (NCT) Identified Number: Pending

Principal Investigator:

[name]; Allergy and Immunology and Food Allergy Center

Co-Investigators:

[name]; Allergy and Immunology and Food Allergy Center

[name]: Allergy and Immunology

Sponsor: The University of Michigan

Funded By: Gerber Foundation

Version Number: 2.2

30 August 2023

Statement of Compliance

The trial will be carried out in accordance with International Conference on Harmonization Good Clinical Practice (ICH GCP) and the following:

- United States (US) Code of Federal Regulations (CFR) applicable to clinical studies (45 CFR Part 46, 21 CFR Part 50, 21 CFR Part 56, 21 CFR Part 312, and/or 21 CFR Part 812)

Investigators and clinical trial site staff who are responsible for the conduct, management, or oversight of clinical trials have completed Human Subjects Protection and ICH GCP Training.

The protocol, informed consent form(s), recruitment materials, and all participant materials will be submitted to the Institutional Review Board (IRB) for review and approval. Approval of both the protocol and the consent form must be obtained before any participant is enrolled. Any amendment to the protocol will require review and approval by the IRB before the changes are implemented to the study. In addition, all changes to the consent form will be IRB-approved; a determination will be made regarding whether a new consent needs to be obtained from participants who provided consent, using a previously approved consent form.

Protocol Summary

Synopsis

Title: Transepidermal Water Loss as a Predictor for Severe Allergic Reactions in Oral Food Challenges

Study Description: This is a pilot clinical trial, which will test the hypothesis that transepidermal water loss (TEWL) measured continuously during an oral food challenge (OFC) for peanut food allergy predicts the development of anaphylaxis such that stopping the food challenge early based on this change will reduce the rate of anaphylaxis during such food challenges.

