Outcome measures. The outcome measures collected for each group in Table 2 show the hypothesized relationship for each group. If a stopping rule is implemented, that will be considered a positive challenge. We hypothesize that the intervention group will have lower anaphylaxis rates and/or severity via earlier OFC stoppage and earlier time to or more frequent treatment with non-epinephrine medications (such as antihistamines). We suspect the overall reaction rate will remain the same, but that these reactions will not devolve into anaphylaxis in the intervention group due to the above factors. Anaphylaxis will be defined according to current practice parameters ⁷², which is broadly considered to be at least two symptoms consistent with allergic reactions (cutaneous, gastrointestinal, respiratory, elevated heart rate, among others) or a decrease in blood pressure.

Post-OFC

1. Participants without evidence of an allergic reaction during the OFC will receive a follow-up phone call 1 day after the OFC to follow up on any additional symptoms or concerns.

2. Participants that had a reaction will be scheduled for a follow-up call within 1 day of the OFC to assess for additional symptoms or resolution of symptoms per the standard of care.

c. Subject Withdrawal

- i. Under what conditions will a subject be withdrawn prior to completion
- ii. If a subject withdraws prior to completion, what is the plan for the use of their data

Any subject may withdraw at any time for any reason. These reasons may include but are not limited to:

- Subject's request, no reason needed
- Adverse event – at Investigator's request. Potential examples include concern that proceeding further would impose unanticipated risk not otherwise delineated here or for any reason that continued participation could impact study integrity.

The data for any subject who withdraws prior to completion will be flagged as incomplete data in our data set. We will delete data if the subject requests this.

d. Data Retention and/or Data Destruction Plan

- i. How long will you keep subject data?
- ii. If you plan to destroy the data, how will you destroy it?

Data collected will be retained for study record keeping purposes and for future research use for up to 5 years or in accordance with our sponsor's policies. Thereafter, data will be fully de-identified fully and retained indefinitely. No data will be destroyed.

Risks & Benefits

- a. What are the risks and what will be done to monitor the risks?

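### The protocol body is inconsistent on what halts dosing in each arm, and the 80% and 30% planning rates are not tied to any one reading

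*Combined protocol and SAP*

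**What the plan says.** The statements on halting are spread over several sections of the combined protocol and SAP.

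- **Synopsis, Study Description.** The hypothesis is that "stopping the food challenge early based on this change will reduce the rate of anaphylaxis during such food challenges", the change being in TEWL.
- **Synopsis, Description of Study Intervention.** For both arms: "In both cases, the standard of care will be used, where even a single symptom of an allergic reaction is used to stop" the challenge.
- **Primary Objective.** The contrast is named as TEWL stopping rules plus standard clinical assessment against clinical assessment only.
- **Blinding procedures.** The coordinator needs to know the arm "to declare the OFC ceased when stopping rules are reached". No symptom condition is mentioned here.
- **Adjudication of OFC results.** The threshold is a planned rise of 1 g/m²/h, comparing two-minute averages after and before a dose. Then: "If the individual meets this threshold, at the first sign of a clinical symptom, the food challenge will be stopped".
- **Treatment of reactions.** After a reaction short of anaphylaxis, "the physician may choose to stop the OFC and give an antihistamine". Once the TEWL rule is invoked, dosing ends; epinephrine is given if anaphylaxis criteria are met, "otherwise an antihistamine dose will be given per standard of care".
- **Outcome measures.** The expected benefit comes from earlier stopping and from earlier or more frequent non-epinephrine treatment, with the overall reaction rate expected to stay the same.
- **Statistical Design, Population size.** Anaphylaxis is assumed at 80% in control and 30% in intervention, with Fisher's exact test, two-sided alpha 0.05 and 80% power. This gives 19 per group, or 40 enrolled after 5% drop-out.
- **Benefits to the individual.** An estimated 20% of both groups will pass the challenge.

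**The concern.** The primary comparison estimates the effect of a stopping rule, so the reader must be able to say what differs between the arms. The Synopsis and the definition of the TEWL rule, followed literally, leave no difference in when dosing stops: every stop that the TEWL rule triggers occurs at a first symptom, and a first symptom already stops the challenge in both arms. Treatment of reactions describes something else, a discretionary stop in usual care against a mandatory one under the rule.

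If this is left unreconciled, a result could not be attributed with confidence to one defined rule. The planning rates would also rest on an unspecified contrast, and the power statement holds only if the rule actually used produces them.

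**Working it through.** **1. The halting statements side by side**

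| Section | Control arm | TEWL arm |
|---|---|---|
| Synopsis, Study Intervention | Single symptom used to stop | Same |
| Adjudication of OFC results | – | Threshold met, then stop at first symptom |
| Treatment of reactions | Physician may stop after a non-anaphylactic reaction | Stop once rule invoked; antihistamine if no anaphylaxis |
| Blinding procedures | – | Coordinator declares stop when rule is reached |
| Synopsis, Study Description | – | Early stop based on the TEWL change |

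Rows 1 and 2 together: stop timing is the same in both arms, and treatment after the stop may still differ. Rows 2 and 3 together: mandatory against discretionary stopping, plus antihistamine. Row 5 alone can be read as a stop on TEWL without a symptom. Row 4 refers to a rule without defining one.

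**2. The plan's sample size**

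Inputs from Population size: 0.80 against 0.30, two-sided alpha 0.05, 1:1. Exact power is the sum, over all pairs of event counts (a, b), of Bin(a; n, 0.80) × Bin(b; n, 0.30), counting only pairs with two-sided Fisher p ≤ 0.05.

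| n per arm | Exact power |
|---|---|
| 17 | 79.2% |
| 18 | 83.5% |
| 19 | 85.2% |
| 20 | 84.6% |

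The continuity-corrected formula gives 19 per arm, exactly as stated, and 38 / 0.95 = 40. The plan's figure is reproduced.

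**3. What the two rates imply**

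With 20% passing in both groups, 1 − 0.20 = 80% react.

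- Control: 0.80 / 0.80 = 100% of reactors reach anaphylaxis.
- Intervention: 0.30 / 0.80 = 37.5% of reactors do.
- Anaphylaxis averted by the rule: 1 − 0.30 / 0.80 = 62.5%.

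Per 20 children:

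| Arm | Pass | Anaphylaxis | Non-anaphylactic reaction |
|---|---|---|---|
| Control | 4 | 16 | 0 |
| Intervention | 4 | 6 | 10 |

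The zero in the control row sits poorly with single-symptom stopping in the Synopsis, and with the remark in Table 1 that many challenges are stopped on a non-anaphylactic reaction.

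**4. How much room the power statement has, at 19 per arm**

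- Control held at 80%: power is 80.0% at an intervention rate of 33.0% and 79.1% at 33.5%.
- Intervention held at 30%: power is 81.2% at a control rate of 78% and 79.1% at 77%, crossing 80% at 77.4%. As a share of reactors, 77.4 / 80 = 96.8%, so the crossing comes once about 3% of control reactors stop short of anaphylaxis.

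For illustration only, with assumed control rates and intervention held at 30%:

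| Control reactors stopped before anaphylaxis (assumed) | Control rate | Power |
|---|---|---|
| 12.5% | 70% | 62% |
| 25% | 60% | 37% |
| 37.5% | 50% | 17% |

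The documents do not say that any of these rates will occur.

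**The case against.** The strongest reply is that a coherent reading exists. The Primary Objective names the contrast, Treatment of reactions shows how it could operate, and the Synopsis sentence can be taken to mean that a single symptom permits a stop. This stands as a possible reading, and it is why the contrast cannot be called undefined. But the Synopsis does not say it, and the reader has to choose it.

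A reader might infer that the protocol contains a rival rule, a stop on TEWL alone. The documents do not support that firmly. Only Adjudication of OFC results defines the rule, and it includes the symptom. Blinding procedures and Treatment of reactions merely do not repeat it. A TEWL-alone stop would also strain the expectation of an unchanged reaction rate and of 20% passing in both groups, because an implemented stop counts as a positive challenge.

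A reader might also infer that the Synopsis and the rule definition make the arms identical, with no expected effect. That goes too far. Antihistamine follows the TEWL stop but is optional after other non-anaphylactic reactions, and more frequent treatment is one of the stated mechanisms.

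On the rates, the 20% is an estimate from the benefits section, stopping doses does not guarantee that a reaction stops progressing, and the children have a history of peanut anaphylaxis. The Background describes challenge reactions as typically anaphylaxis, and the adverse event section expects it in most of these challenges. So 100% of control reactors is a tension and not a contradiction. The 3% margin is about half a child (19 × 0.80 = 15.2 against 19 × 0.774 = 14.7) and depends on holding the intervention rate at 30%. If the 62.5% relative reduction is kept instead (an assumption), 76% against 0.375 × 76% = 28.5% still gives about 80% power, a margin of 4 / 80 = 5% of control reactors.

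Finally, the clinical OFC appendix was not in the text available for this review. It may settle what usual care means; the body would still need to agree with it.

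**Conclusion.** The concern holds as an inconsistency in the protocol body. The single-symptom statement and the physician's discretion do not agree, and the single-symptom statement combined with the definition of the TEWL rule removes the earlier stopping on which the hypothesis partly rests. One workable contrast can be assembled, but no section says that it governs, and the 80% and 30% rates are tied to none.

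The sample size is not in error. It is right for its inputs, and the break-even points of about 33% and 77% show how little those inputs can shift; they are not predictions. The tension between 80% control anaphylaxis and a 20% pass rate rests on taking both planning figures at face value.

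A reader might further infer that the TEWL threshold is still unset, because Statistical Design describes it as something to be derived from data. The 1 g/m²/h value may simply be the output of that derivation. This is a secondary clarification. Which clinical rule should apply is not judged here.

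**What to change.** Reconcile the Synopsis (Study Description and Study Intervention), Blinding procedures, Adjudication of OFC results, Treatment of reactions, Outcome measures and the clinical OFC appendix into one statement per arm of what halts dosing and what treatment follows. The choice of rule belongs to the investigators.

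Then confirm in Population size that 80% and 30% are the rates expected under that rule and that they fit the 20% pass rate. If they do not, restate the assumed rates and the power at n = 40. As a secondary point, say whether the 1 g/m²/h value is the final output of the derivation described in Statistical Design.

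The cost is a wording amendment and instruction of the coordinator, nurse and physician, with no added procedures or children. The possible downside is a less favourable stated power.
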